8.2 Screening & Enrollment	
9. FUNDING	. 22
10. PUBLICATIONS	. 22
11. DATA SHARING	. 22

12. INTELLECTUAL PROPERTY	22
13. TASKS AND RESPONSIBILITIES	22
Appendices	23
Appendix 1: Abbreviations	23
Appendix 2: Screening Questions	23
Appendix 3: Baseline Questions	25
Appendix 4: SMS Run-In	28

SYNOPSIS

The "Safe Vehicle Engagement (SaVE)" trials are 3 parallel randomized clinical trials that aim to determine the impact of text messaging (SMS) vehicle safety interventions vs. weekly SMS vehicle safety self-monitoring alone on seat belt use, distracted driving and drink driving among young adults identified in the emergency department with risky vehicle behaviors.

TRIAL OVERVIEW

Title	Utilizing Text Messaging to Improve Vehicle Safety Behavior Among At-Risk Young Adults – 3 Parallel Randomized Controlled Trials (The SaVE Trials)
Clinical Trials Number	NCT
Sources of monetary or material support	NHTSA
Study Sites	2-sites in the United States (Pittsburgh & Philadelphia)
Conditions studied	Seat belt use, distracted driving, drink driving
Interventions	Text messaging (SMS) intervention: vehicle safety self- monitoring with performance feedback and goal support
Comparator	SMS vehicle safety self-monitoring
Inclusion criteria	 Young adult (age 18-25 years) Cohort 1: Any vehicle trip in past 2 weeks where individual reports not using a seat belt Cohort 2: Any vehicle trip in past 2 weeks where individual reports phone was used to type while driving and car was moving Cohort 3: Any vehicle trip in past 2 weeks where individual reports driving a vehicle within 3 hours after consuming 3 or more drinks
Exclusion criteria	 Member of a protected population (prisoner) Unable to provide informed consent No plan to drive and/or ride in a vehicle in the next month Non-English speaking No personal mobile phone or planning on changing phone in next 3 months
Study type	Interventional Assessment-only run-in (2-week) Allocation to trial cohort : Computerized algorithm to preferentially allocate to seat beltcohort Allocation to treatment : Randomized (1:1) Intervention model: Parallel group Masking: Assessor-blinded
Target sample size	500 Participants • Cohort 1 : N=300 • Cohort 2 : N=100 • Cohort 3 : N=100
Primary outcome (week 8)	 a. Cohort 1: Any vehicle trip in past 2 weeks where individual reports not using a seat belt b. Cohort 2: Any vehicle trip in past 2 weeks where individual reports phone was used to type while driving and car was moving

	 Cohort 3: Any vehicle trip in past 2 weeks where individual reports driving a vehicle within 3 hours after consuming 3 or more drinks
Key secondary outcomes	Effectiveness-Primary outcomes at week 14 (durability)Feasibility-Percentage of ED patients who screen positive and agree to enrollPercentage of ED patients who enroll who meet run-in criteria.Acceptability-Percentage of ED patients enrolled in the Intervention arm who complete at least 50% of the SMS assessments during the intervention periodPercentage of ED patients enrolled in the Intervention arm who found the program helpful.

STEERING COMMITTEE

[name].

Assistant Professor of Emergency Medicine University of Pittsburgh School of Medicine

[name].

Assistant Professor of Emergency Medicine University of Pennsylvania School of Medicine

[name]

American College of Emergency Physicians Emergency Medicine Foundation

[name].

Assistant Professor of Nursing University of Pennsylvania School of Medicine

[name] , Ph.D.

[name] of Michigan

[name]

Director of Grant Development American College of Emergency Physicians Emergency Medicine Foundation

Conflicts of interest

The members of the steering committee have no financial conflicts of interest related to the current trial.

TRIAL SITES

Coordinating Center University of Pittsburgh

Department of Emergency Medicine Site Investigator: [name]

Enrolling Sites*

Hospital Name	Location	Site Principal Investigator
UPMC Mercy Hospital	Pittsburgh, PA	[name]
UPMC Passavant Hospital	McCandless, PA	[name]
Hospital of the University of Penn	Philadelphia, PA	[name]
Penn Presbyerian Hospital	Philadelphia, PA	[name]

*Depending on study progress, sites may be added or removed in the future.

1. BACKGROUND AND SIGNIFICANCE

1.1 Scope of the Problem

There were around 25,0000 people killed inside vehicles on U.S. roadways during 2016 (NHTSA, 2016) and over 2 million injured in motor vehicle crashes (MVC) (CDC, 2016). A few key behaviors contribute to increased risk of either MVCs or MVC-related injuries: lack of seat belt use, impaired driving (due to drugs and/or alcohol), and distracted driving (due to either other passengers or electronic devices). Among the deaths from MVCs in 2016, 42% were unrestrained passengers (NHTSA, 2016). These behaviors are especially prevalent in young adults. Over 35% of lifetime medical costs for crash injuries (US\$6.5 billion of US\$18 billion) are attributed to young drivers aged 15 to 29 (CDC, 2014).

1.2 Existing Vehicle Safety Interventions

To date, most primary prevention interventions for young adult vehicle safety have been through multimedia campaigns (Whittam KP et al., 2006), driver training programmes (Lenne LG et al., 2011; Unni P et al., 2017), or public policies such as surveillance with fines for speeding and seat beltuse (Wilson C et al., 2011). Secondary prevention approaches include mandated interventions for offenders such as alcohol Ignition Interlocks (McGinty EE et al., 2017). Recently, improved knowledge of the behavioral drivers of vehicle safety allow for updated interventions incorporating psychological theories and behavior change techniques (Fernandez et al., 2010).

1.3 Behavioral Drivers of Vehicle Safety

Two psychological theories useful in understanding vehicle safety behaviors are the Theory of Planned Behaviour (TPB) and the Health Belief Model (HBM). In the TPB, intentions are influenced by a person's attitude, perceived norms and self-efficacy. The TPB has been shown to explain up to 53% of variance in intention to speed and 40% of variance in speeding behavior (Stead M et al., 2005). In the HBM,the perceived risks/threats of personal injury and the perceived benefits of performing a safety behavior influence the likelihood of performing them. These HBM factors have been shown to be important in sealt belt use (Chaudhary, Solomon, & Cosgrove, 2004; Helweg-Larsen & Sheppard, 2001).

1.4 Existing Interventions Targeting Cognitive and Motivational Factors of Vehicle Safety

Among the few studies have been published testing behavioral interventions for vehicle safety, several have shown that these cognitive and motivational factors of vehicle safety behaviors can be potentially modified. One study showed that an intervention targeting TPB factors resulted in small immediate improvements in vehicle safety (Poulter DR et al., 2010) but effects were not durable over time. Another study by McDonald et al (2018) reported on the development of a digital intervention targeting TPB factors, finding feasible and initial evidence of effects.

1.5 Rationale for SMS Behavioral Interventions

In the US, mobile phones are near ubiquitous, and by the year 2020, 70% of the world's population will use a smartphone (Ericsson, 2015). Text messaging (SMS) is a commonly used digital communication modality that has particular usefulness in reaching individuals to support behavior change (Suffoletto et al.,2017). SMS interventions are ideally suited to deliver microinterventions—interventions that can be completed in a few moments, typically as a repeated administration, tailored to some immediate assessed need or trigger. These microinterventions are more closely in line with the expectations of consumers of digital information, who may routinely interact with fast-paced, user-driven, interactive content. Systematic reviews have found SMS interventions to be effective in short-term behavioral outcomes (Fjedsoe et al., 2009) and supporting preventive health for adolescents specifically (Badway & Kuns, 2017). Our group has shown that SMS interventions incorporating behavior change strategies of self-monitoring with performance feedback and goal support produces reductions in alcohol use in at-risk young adults (Suffoletto et al., 2017).

1.6 SMS Interventions to Reduce Risky Vehicle Behaviors

In this proposal, we plan to design and test three unique SMS interventions each targeting a different vehicle risk behaviors (seat belt use, distracted driving, and impaired driving). They will all use psychological theory and state of the art human-interaction design to optimize engagement and effects. Specifically, the SMS interventions will incorporate periodic (weekly) check-ins to promote self-monitoring of recent risks, goal commitment prompts tailored to past performance to maximize willingness and support gradual behavioral shaping, and performance feedback. Feedback and features will focus on modifying cognitive and motivational factors found in the TPB amnd HBM.

2. TRIAL DESIGN

2.1 Overview

We propose to conduct 3 related randomized, controlled, parallel group, assessor-blind, superiority trials of 6-week text message interventions vs. SMS vehicle safety self-monitoring in young adult participants with risky vehicle behaviors. A total of 500 adult participants will be enrolled: 300 into Cohort 1 (seat belt); 100 into Cohort 2 (distracted driving); 100 into Cohort 3 (drink driving). Each SMS intervention will be desgined to target a single risk behavior. The study is powered to show a difference of 15% in the percentage of subjects reporting seat belt use at week 8. Other cohort trials (i.e. distracted driving, drink driving) and outcomes will be exploratory.

2.2 Setting

The trial will be conducted at 4 hospital emergency departments in Pennsylvania. Additional sites might be recruited if needed.

2.3 Inclusion criteria

Inclusion criteria:

- 1) Adult participant (age \geq 18 years & \leq 25 years)
 - a. Cohort 1: Any vehicle trip in past 2 weeks where individual reports not using a seat belt
 - b. Cohort 2: Any vehicle trip in past 2 weeks where individual reports phone was used to type while driving and car was moving
 - c. Cohort 3: Any vehicle trip in past 2 weeks where individual reports driving a vehicle within 3 hours after consuming 3 or more drinks

Exclusion criteria:

- 1) Member of a protected population (prisoner)
- 2) Unable to provide informed consent
- 3) No plan to drive and/or ride in a vehicle in the next month
- 4) Non-English speaking
- 5) No personal mobile phone or planning on changing phone in next 3 months

Justification of Inclusion and Exclusion Criteria: The inclusion criteria were chosen to isolate three different vehicle risk behaviors in a population with high risk of injuries due to these risks. We chose to be more inclusive than restrictive in these criteria to ensure me meet enrollment goals in the allotted time of funding. The exclusion criteria were chosen to minimize the risk of potential harm to vulnerable populations.

2.4 Participant Identification

In the ED a research associate (RA) will conduct confidential screening of ED patients during breaks in patient medical care. The RA will review ED admissions data form the EMR to identify potential subjects, identifying adult patients 18-25 years of age who receive medical care in the ED. The RA will then ask a clinician (physicians, nurses, or physician extenders) caring for a potential participant to ask the patient if they are interested in speaking with a researcher about a research study. ED clinicians are instructed to refer only patients who are able to provide informed consent (i.e., oriented, able to concentrate, not intoxicated and can understand/remember requirements of the study). We ask clinicians to document in their medical record about the patient's assent to talk with the RA.

The RA will then discuss the screening and study details with these patients who agree to be approached. Those who wish to see if they are eligible will be asked to complete limited demographics (age, sex, race, and current education), a 13-question screening test to determine presence of vehicle risks using a secure password-protected website. The demographics will be

used to determine how those who screen and/or enroll in our study differ from the general ED population of young adults. *See Appendix for Screen Questions*.

All participants who are screen positive will be provided an information sheet on vehicle risk reduction. *See Appendix for draft of Discharge Instructions*. We will request a waiver of informed consent to view the electronic medical record to identify potential participants by age and a waiver of written consent to ask limited screening questions. Detailed screening logs, with reason(s) for exclusion will be stored in a password-protected database.

2.5. Consent procedures

After it is determined that they meet all inclusion criteria and no exclusion criteria, the participant will be approached for written informed consent by a RA. The RA will provide the participant/representative information regarding the background and significance of the study, eligibility criteria, and a description of the protocol. The consent process may need to be modified based on site-specific IRB recommendations. The name of the study investigator obtaining consent will be clearly documented, and this person will sign the informed consent document and provide the date and time of their signature. Signed copies of the consent form will be given to the participant/surrogate, and the original consent document will be stored in the secure study file. In obtaining and documenting informed consent, each investigator will comply with the applicable regulatory requirements and adhere to the ethical and Good Clinical Practice principles that have their origin in the Declaration of Helsinki.

2.6 Contact Information

Participants will be asked to provide us with their contact information (name, phone number, email). We will also ask them to provide a social security number, as it is required for participant payment.

2.7 Allocation to Cohorts

We will use the risks reported in the screening survey to allocate the participant to their cohort. The overall goal is to meet recruitment goals for all three cohorts simultaneously, but to preferentially allocate individuals to the seat belt group (Cohort 1). Individuals who report only one risk behavior will be allocated to that study cohort. Individuals who report more than one risk factor will be allocated probabilistically. Individuals who screen positive for seat belt risk + one other risk will have a 75% chance of being allocated to Cohort 1. Individuals who screen positive for seat belt risk + two other risks will be allocate as 60% Cohort 1, 20% Cohort 2, 20% Cohort 3. Individuals who screen positive for both other (non-seat belt) risks will be allocated in a 1:1 ratio.

2.8 Baseline Assessment

We will ask participants to complete a questionnaire collecting detailed demographics, vehiclerelated risks, and impulsivity traits. This survey takes about 5 minutes to complete *See Appendix for Survey Questions*. We will also ask participants to complete the 5-Trial Adjusting Delay Discounting Task (Kaffaurnus & Bickel, 2014) to assess monetary impulsivity trait. All cohorts will complete identical baseline assessments.

2.9 SMS Onboarding

We will then ask participants to text in a keyword to our program phone number. Only phone numbers that match the phone numbers entered by the RA in the enrollment process wil receive texts. Once this match is recognized, participants will receive several texts welcoming them to the study and describing the 2-week run-in. Each chohort will receive similar yet unique welcome messages tailored to their risk behavior.

2.10 SMS Run-in

All participants will complete a 2-week run-in period where they complete weekly SMS assessments related to their target risk behavior without receiving any feedback or goal support. The primary purpose of the run-in is to exclude noncompliant subjects. Only participants who respond to at least 50% of the SMS queries in week 1 & 2 will be eligible to continue in the study. The secondary purpose is to identify the post-enrollment/ pre-intervention vehicle risk behaviors that may occur as a result of assessment reactivity. We expect that simply the act of enrolling in a study about vehicle risk and completing weekly SMS assessments of risk may result in reduced risk behaviors.

2.11 Allocation to Treatment

Participants in each cohort who meet run-in criteria will be randomized in a 1:1 ratio to either the SMS intervention or SMS self-monitoring in blocks of 4. The randomization will be stratified according to site (i.e. ED). An independent statistician will create the randomization list using a random number generator. The randomization list will be stored in an electronic database to be unblinded once trial enrollment and follow-up periods have been completed.

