2.14 Outcome Assessments & Blinding

The primary outcomes will be the percentage of participants in each treatment arm who report vehicle risks at week 8 (immediate effects) and week 14 (durable effects). Questions are the same as those used in screening. Participants will receive a text prompting them to log in to the secure web site to complete the 21-question survey which should take them no more than 10 minutes to complete. Research associates and investigators will be blinded to the allocation until outcome evaluation. It is not possible to blind subjects given the nature of the intervention. We do not expect any scenarios where emergency unblinding will be necessary.

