6.2.2 Protection Against Risk: In order to protect study participants form potential risks related to the loss of confidentiality and due to any discomfort that they may experience in answering any questions, the following steps will be taken: 1) Patients will be told that they can withdraw from the study at any time by contacting us. 2) All information provided by the patient will be referenced to a subject ID# and will be kept in locked file cabinets. The patient's ID# can be connected to the subject's name only through a single master file, accessible only by the Primary Investigator. All data and files will be entered on computers protected by passwords and stored in a locked office. 3) All research staff will be trained in the importance of maintaining confidentiality and will undergo annual mandatory training of human subjects research. 4) All patient data will be presented in aggregate and no individuals will be identified individually. Additionally, we will make every effort to ensure that subject information is protected so only

SaVE Trial Protocol v.1.0 Page **19** of **36** authorized persons can see their information. All messages sent from subjects to our phone number will be catalogued and encrypted, stored per UPMC security standards. All participants will be advised to set up password protection on their cell phones and to erase messages after responding to minimize the chance of loss of private information. We state explicitly in the consent that we will not be able to respond in real-time to any concern a patient has that is outside the expected responses that is sent to our phone number, nor any text message outside the scope of the question we ask. Immediate or emergency text-messages that are received and outside the scope of the questions we sent will all receive a standardized text message, stating "We appreciate your participation. If you have an emergency, please call 911." As well, all messages are archived in our database and will be reviewed at least every 2 days by the investigators. At the end of this study, the data key will be destroyed.

6.2.3 Certificte of Confidentiality: Because we are collecting data that is sensitive, we will seek a Certificate of Confidentiality from the NIH.

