13. TASKS AND RESPONSIBILITIES

Principal investigator: Overall responsibility for protocol development, intervention development, budget overview, data dictionary development, ethical approval, trial registration, daily management, trial oversight and collection of adverse events, and the data and safety monitoring board, assessment of overall recruitments, potential recruitment of additional sites, data analysis, and dissemination and presentation of results.

Co-Investigators: Site-specific enrollment, education of personnel at participating sites, reporting of site-specific issues or challenges to the principal investigator, participant consent for data collection, collecting and reporting data regarding adverse events. Also protocol development, data dictionary development, trial oversight, dissemination of results.

Steering committee: Protocol development, data dictionary development, trial oversight, dissemination of results.

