Appendix: SMS Interventions: TWD Safety

	Incomi	
Day & Time	ng	Outgoing
Qualified Week 3, Monday, 5pm		
Qualified [At least 1 Sunday Assessment complete]		Congratulations [Name]! You have qualified to continue the SaVE Study
· · · · · · · · · · · · · · · · · · ·		For the next 6 weeks, we will help you set goals and provide you personalized feedback on your driving safety
		We will check in next Sunday. Until then, take care.
Week 3-8: Sunday, 3pm		
2 hours	[Missin g] x1	Hi [_NAME_], it's the SaVE Study Team checking in. How often have you driven a car the past week? 0=never; 1=a few times; 2=most days; 3=every day We missed your response. Text us how often you have been a passenger or driver in a car the past week?
2 110013	[Missin	car the past week:
2 hours	g] x2 [Nonse nse]	You must be busy. We will check in tomorrow. We don't understand. Please text us a response option: 0=never; 1=a few times; 2=most days; 3=every day
1 hour	0 1,2,3 [Missin g] x1	OK. When driving, how often did you type on your phone when the car was moving? 0=never; 1=a few times; 2=most of the time; 3=every time We missed your response. Text us how often did you type on your phone while the car was moving
Thou	[Missin	was moving
1 hour	g] x2 [Nonse nse]	You must be busy. We will check in tomorrow. We don't understand. Please text us a response option: 0=never; 1=a few times; 2=most of the time; 3=every time
If Goal Not Set	0	[Posiitve Reinforcement Message]
	1,2,3	[Social Norms Message]
If Goal Set	Goal met Goal	[Goal Met Message]
	not met	[Goal Not Met Message]
		Would you be willing to commit to a goal to refrain from typing on your phone while driving this week?
1 hour	[Missin g] x1 [Missin	We missed your response. Text us whether you'd be willing to set a goal?
1 hour	g] x2 [Nonse	You must be busy. We will check in later.
	nse]	We don't understand. Please text us either yes or no
No Goal	No	[No Goal Roll Library Message]
Goal +	Yes	[Goal Reinforcement Message]
Random 2 days per week, 4pm		
lf goal -		[Distracted Driving Info Message]
If goal +		[Goal Reminder Message]

SaVE Trial Protocol v.1.0 Page **31** of **36**

Incoming	Outgoing
	Congratulations [Name]! You have qualified to continue the SaVE Study
	For the next 6 weeks, we will help you set goals and provide you personalized feedback on your driving safety
	We will check in next Sunday. Until then, take care
	Hi [_NAME_], it's the SaVE Study Team checking in

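### One fixed block size of 4 is printed in the protocol while investigators read arm-revealing texts: up to one third of assignments are certain at the draw, a limited exposure that is cheap to close

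*Combined protocol and SAP*

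**What the plan says.** All references are to the combined protocol and SAP.

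- **Allocation (2.11).** Participants in each cohort who pass the run-in are "randomized in a 1:1 ratio to either the SMS intervention or SMS self-monitoring in blocks of 4", with stratification by ED. An independent statistician makes the list, and it stays closed until enrolment and follow-up end. No varying or undisclosed block size is mentioned.
- **Sites (2.2).** "The trial will be conducted at 4 hospital emergency departments in Pennsylvania". With three cohorts, that makes 12 ED-by-cohort strata.
- **Blinding (2.14).** For participants, "It is not possible to blind subjects given the nature of the intervention". The same section says that research associates and investigators stay blinded until outcome evaluation.
- **Message review (6.2.2).** "all messages are archived in our database and will be reviewed at least every 2 days by the investigators". No role is excepted.
- **What the texts show (2.12, 2.13 and the SMS intervention appendices).** Goal prompts and feedback go only to the intervention arm. Controls get assessment questions alone.
- **Enrolment (13, 2.4, 2.5, 6.2.1).** Co-investigators are responsible for "Site-specific enrollment, education of personnel at participating sites". Research associates screen and approach patients for consent, although 2.5 also refers to a study investigator who obtains consent and signs the form.
- **Gate before the draw (2.10 and the TWD script).** The text of 2.10 reads "Only participants who respond to at least 50% of the SMS queries in week 1 & 2 will be eligible". The typing-while-driving (TWD) script marks qualification as "At least 1 Sunday Assessment complete".

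**The concern.** Allocation concealment requires that nobody who influences entry knows the next assignment. With a published block of 4, a person who knows the earlier arms in the current block knows the fourth for certain, and the third whenever the first two match. Keeping the list closed does not prevent this.

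The knowledge comes from the message review in 6.2.2, which shows arms directly and so contradicts the blinding stated in 2.14. Some of the people given that review, the co-investigators, also have responsibility for enrolment. Participants are unblinded and the primary outcome is self-reported, so concealment is one of the main protections the comparison has left. If entry were influenced by a predicted assignment, the arms could differ in readiness to change before treatment starts.

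**Working it through.** The documents give no figure for predictability, so there is none to reproduce. The attrition inputs do reproduce: 4.1 expects 10% loss in the run-in and 80% completing week 8, and 300 x 0.9 x 0.8 = 216, as stated there.

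**1. Ceiling: all earlier assignments in the block known.** There are 6 balanced sequences of two and two, hence 24 draws.

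| Position in block | Chance the draw is certain | Chance the best guess is right |
|---|---|---|
| 1 | 0 | 1/2 |
| 2 | 0 | 2/3 |
| 3 | 1/3 | 2/3 |
| 4 | 1 | 1 |

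- Certain: (0 + 0 + 1/3 + 1)/4 = 8/24 = 33.3%. This agrees with 2/(b + 2) for block size b = 4.
- Guessed correctly: (1/2 + 2/3 + 2/3 + 1)/4 = 70.8%, against 50% by chance.

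**2. Most recent assignments in the stratum not yet known.**

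| Latest assignments unknown | Certain | Guessed correctly |
|---|---|---|
| 0 | 33.3% | 70.8% |
| 1 | 2/24 = 8.3% | 58.3% |
| 2 | 0% | 54.2% |
| 3 | 0% | 50.0% |

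**3. Allowing for the weekly schedule.** The qualifying text is scripted for Monday of week 3 at 5pm, so draws are taken to come in Monday batches. Members of the same batch do not inform each other. The first goal prompt follows on Sunday at 3pm. Section 6.2.2 does not say whether review covers outgoing texts.

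- If it does, the qualifying text, which announces goals and feedback, shows the arm within about 2 days and before the next Monday.
- If only replies are read, the first goal reply may be seen after the next Monday's draw.

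Assumptions: Poisson accrual, equal EDs, and the 10% run-in loss of 4.1 applied to all cohorts. That gives 300 x 0.9/4 = 67.5, about 68 per ED in Cohort 1, and 100 x 0.9/4 = 22.5, about 22 per ED in Cohorts 2 and 3. Accrual is taken over 26, 52 and 78 weeks. Simulated share of certain draws:

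| Arms known by | Cohort 1 | Cohorts 2 and 3 |
|---|---|---|
| Next Monday | 14-25% | 22-27% |
| Two Mondays later | 2-12% | 11-22% |

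**4. What varying blocks would change.** With all earlier assignments known but sizes 4, 6 and 8 used in undisclosed random order, the certain share falls from 33.3% to about 2%. The best guess is still right about 67-68% of the time, against 70.8%. Varying the size removes certainty but does little to guessing.

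**5. The two run-in rules.** Two Sundays with two questions each make 4 queries for someone who drove in both weeks. Answering only the driving question both times is 2/4 = 50%, which passes 2.10, but completes no Sunday assessment. If a query means a whole Sunday check-in, 1 of 2 = 50% and the rules coincide.

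**The case against.** The strongest reply is that prediction has almost nowhere to act. Patients answer the screening questions themselves on a tablet, and research associates approach all potentially eligible patients who agree (6.2.1). Cohort is set by algorithm (Synopsis, 2.7). Consent precedes the draw by about 2 weeks. Run-in pass or fail is a count of time-stamped replies, with a scripted Day 15 withdrawal text. Nothing says that research associates read messages, and 5.4 limits database access to specific faculty and staff. Most of this stands, and it is why the point is minor. It does not remove the point: 6.2.2 gives review to investigators without restriction, section 13 gives co-investigators enrolment, and no section separates the two tasks.

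A second reply is that varying blocks barely lowers guessing. That is correct (step 4), so the block change cannot be the whole remedy.

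Three stronger readings are tempting but unsupported:

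- A reader might infer that one third of assignments will in fact be known. That needs every earlier arm in the block before each draw, which the Monday batches and the delay to the first goal prompt do not allow.
- A reader might infer a materially inflated false-positive rate. Such a figure needs every entrant to be steered on the guess, and an outcome gap between steered groups that the documents do not give. No bias figure is offered here.
- A reader might infer that someone exercises judgement at the run-in decision. The differing rules leave a borderline case unresolved, but no section describes human discretion over it.

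**Conclusion.** The point holds as a low-severity weakness in concealment. The firmest part needs no arithmetic: 2.14 says investigators are blinded, and 6.2.2 has them read messages that show the arm. Added to that, a single printed block size makes up to 33.3% of draws certain and 70.8% guessable if the whole block is known. The certain share falls to somewhere between 2% and 27%, depending on cohort, accrual speed and how soon the arm is seen. Those lower figures rest on assumed Poisson accrual over 26 to 78 weeks, equal EDs, 10% run-in loss in every cohort and Monday draws.

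The certain share is larger in Cohorts 2 and 3, which 2.1 treats as exploratory. The documents do not show that any assignment would be acted on.

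**What to change.** - **Section 2.11.** Replace the fixed block size with randomly permuted blocks of randomly varying size, stratified by ED within cohort. The independent statistician holds the sizes (for example 4, 6 and 8 in random order), and they are not disclosed in the protocol.
- **Section 2.10 and the TWD script.** Reconcile the two pass rules into one for all cohorts, stating what counts as a query. Have the program record and lock pass or fail by that rule before it draws the assignment.
- **Sections 2.14 and 6.2.2.** Reconcile them by giving message review to existing study personnel with no role in enrolment or outcome assessment. This part is essential, because varying the blocks leaves guessing at about 67-68% for anyone who still sees the arms.

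Cost: a few sentences, a regenerated list before enrolment starts, and a reassigned review task, with no added participants. The statistical downside is a slightly larger possible imbalance within a stratum: up to 4 in an unfinished block of 8, against 2 in a block of 4.
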